### 5.1. Background

Spinal muscular atrophy is a neurogenetic disorder caused by a loss or mutation in the survival motor neuron 1 gene (*SMN1*) on chromosome 5q13, which leads to reduced SMN protein levels and a selective dysfunction of motor neurons. Spinal muscular atrophy is an autosomal recessive, early childhood disease with an incidence of approximately 1: 10,000 live births [1]. Spinal muscular atrophy is the leading cause of infant mortality due to genetic diseases. Disease severity and clinical prognosis depends on the number of copies of survival motor neuron 2 gene (*SMN2*). In its most common and severe form (Type 1), hypotonia and progressive weakness are recognized in the first few months of life, leading to diagnosis before 6 months of age and early death due to respiratory failure before 2 years of age. Motor neuron loss in SMA Type 1 is profound in the early post-natal period (or may even start in the prenatal period), whereas motor neurons in SMA Type 2 and Type 3 patients adapt and compensate during development and persist into adult life. The findings from various neurophysiological and animal studies have shown an early loss of motor neurons in the embryonic and early post-natal periods [2,3,4]. From a clinical perspective, these findings emphasize the importance of first targeting the SMA Type 1 group for gene transfer of *SMN1* in hopes of rescuing neurons at this critical stage. The goal in continuing the development plan for AVXS-101 is to modify the SMA Type 1 phenotype, which will hopefully lead to a milder disease course and prolonged survival as seen in SMA Type 2 and Type 3 patients.

Therapeutic efforts in SMA have focused on the potential for small molecules to increase SMN levels. These include deacetylase inhibitors, such as, valproic acid, sodium butyrate, phenylbutyrate, and trichostatin A. These agents activate the *SMN2* promoter, resulting in

increased full-length SMN protein in SMA animal models [5,6], however, clinical studies employing several of these agents, most notably phenylbutyrate, valproic acid, and hydroxyurea, have not resulted in clinical benefit [7,8]. FDA recently approved Nusinersen, an antisense oligonucleotide (ASO) drug designed to increase the production of the SMN protein by modulating the splicing of the *SMN2* gene, thereby compensating for the underlying genetic defect. Clinical studies have shown some modest promise in improving motor function; however, the treatment must be administered indefinitely on a quarterly basis via intrathecal injection, requires a lengthy induction period prior to effectiveness, and has safety considerations which require clinical monitoring. A single-dose IV administration study of AVXS-101 will provide information on the potential gene transfer has in treating SMA Type 1 patients and will hopefully show promise for success in modifying the disease prognosis.

This is a single-dose study that will include up to 20 Type 1 patients with no functional *SMN1* gene as well as 1 or 2 copies of *SMN2* and who are < 6 months (< 180 days) of age **at the time** of gene replacement therapy (Day 1). The rationale for IV dosing is based upon the need for rapid, systemic impact given the severity of the disease in SMA Type 1 and its potential impact on systems outside of the central nervous system (CNS) such as the peripheral and autonomic nervous systems, heart, pancreas and gastrointestinal tract.

## 5.2. Rationale for Gene Transfer to SMA Type 1 Patients

Patients with SMA Type 1 have been chosen as the target population for this gene therapy study based on studies of the natural history of this disease. The classification of SMA is shown below (Table 4) in which SMA Types 0 to 4 are described. Spinal muscular atrophy is conventionally classified into 4 phenotypes on the basis of age at onset and highest motor function achieved, with an additional phenotype (Type 0) to describe the severe forms of antenatal-onset SMA.

**Table 4: Spinal Muscular Atrophy Classification**

Type	Age at Symptom Onset		Maximum Motor Function	Life Expectancy	SMN2 Copy No.
0	Fetal		Nil	Days – Weeks	1
1	< 6 months	1A: B-2 Weeks 1B: < 3 Months 1C: > 3 Months	Never sits	< 2 years	1, 2, 3
2	6 – 18 months		Never walks	20 – 40 years	2, 3, 4
3	1.5 – 10 Years	3A: < 3 Years 3B: > 3 Years	Walks, regression	Normal	3, 4, 5
4	> 35 Years		Slow decline	Normal	4, 5

Source: Adapted from Kolb 2011 [10]  
*SMN2* = survival motor neuron 2 gene

[figure not shown]
Spinal muscular atrophy Type 1 patients, by definition, never attain independent sitting and have hypotonia within the first 6 months of life. Spinal muscular atrophy Type 1 is the leading genetic cause of infant death with an onset at ≤ 6 month of age (Table 4). In contrast, SMA

Type 2 manifests within the first 18 months, and children afflicted with this condition are able to maintain sitting unassisted but never walk independently. Spinal muscular atrophy Type 3 patients attain the ability to walk unaided (Type 3a have onset 18 months to 3 years of age; Type 3b have onset > 3 years of age). Spinal muscular atrophy Type 4 is an adult onset disease. The genetic cause for SMA is well established and is intimately involved with one's prognosis. All forms of SMA are autosomal recessive in inheritance and are caused by deletions or mutations of the *SMN1* gene.

Humans also carry a second nearly identical copy of the *SMN1* gene called *SMN2* [11]. Both the *SMN1* and *SMN2* genes express SMN protein; however, the amount of functional full-length protein produced by *SMN2* is only 10 to 15% of that produced by *SMN1* [11,12,13]. Although *SMN2* cannot completely compensate for the loss of the *SMN1* gene, patients with milder forms of SMA generally have higher *SMN2* copy numbers [14,15]. Quantitative analysis of *SMN2* copies in 375 patients with Type 1, 2, or 3 SMA showed a significant correlation between *SMN2* copy number and SMA Type, as well as, duration of survival. In a large early study by Feldkotter et al 2002, 2 copies of *SMN2* was 97% predictive for developing SMA Type 1, 3 copies of *SMN2* was 83% predictive for developing SMA Type 2, and 4 copies of *SMN2* was 84% predictive of SMA Type 3 [16]. As these percentages do not reflect the possible impact of modifier mutations such as that described by Prior et al 2009 [17], they may understate the relationship between copy number (in the absence of a genetic modifier) and clinical phenotype. Among 113 patients with Type 1 SMA, 9 with one *SMN2* copy lived < 11 months, 88/94 with 2 *SMN2* copies lived < 21 months, and 8/10 with 3 *SMN2* copies lived 33 to 66 months. Even more refined data describing this relationship has been generated and has also influenced our choice of the study target group.

The severity of SMA Type 1 is demonstrated by prognosis as illustrated in Kaplan-Meier survival curves shown in Figure 1.

**Figure 1: Kaplan-Meier Survival Curves and Survival Probabilities for SMA Types 1, 2, and 3**

n = number of patients

Source: Farrar 2013 [18]

In [Figure 1](#), the relative stability of the clinical course of SMA Type 2 and Type 3 is dramatically illustrated. Perhaps most importantly, these findings show that outcome differences are related to the number of *SMN2* copies that enable motor neurons to adapt and compensate during the growth of the child and persist into adult life. This contrasts with SMA Type 1 where motor neuron loss is profound in the early post-natal period (or may even start in the prenatal period, especially for SMA Type 1 patients presenting in first 3 months of life). The findings in [Figure 1](#) confirm other pieces of evidence from neurophysiological studies and animal studies that also show early loss of motor neurons in the embryonic and early post-natal periods [2,3,4].

There is reason to believe that there are few safety issues to be concerned about when targeting the SMA Type 1 group in this gene therapy clinical study. Overexpression of SMN has been shown to be well tolerated in both mice and non-human primates, and in humans, a high copy number of *SMN2* poses no risk (as seen in Type 2, 3, and 4 patients who have high *SMN2* copy number), allowing for use of robust, ubiquitous expression systems (like the CB-promoter) to ensure sustained, high-level SMN expression. Additionally, it is important to point out that recombinant scAAV can be employed for this study because of the small size of the SMN gene. This enables efficient packaging and allows for efficient gene transfer with lower viral titers (a safety consideration), compared with prototypical single-stranded adeno-associated virus (AAV) vectors.

Recent studies using self-complimentary adeno-associated virus serotype 9 chicken- $\beta$ -actin-hybrid survival motor neuron (scAAV9.CB.SMN) show a robust post-natal rescue of SMN $\Delta$ 7 mice with correction of motor function, neuromuscular electrophysiology and survival after a 1-time delivery of vector [19]. Intravenous scAAV9 is able to transduce neurons, muscle and vascular endothelium, all of which have been proposed as target cells for SMA treatment.

[figure not shown]
### 5.3. Non-clinical Studies

A mouse model was developed by the [REDACTED] after a generation of multiple variants. It was found that the double transgenic, referred to as the SMN $\Delta$ 7 mouse, provided the most suitable model to study gene transfer [20]. Studies performed in the [REDACTED] have shown that injecting  $5 \times 10^{11}$  viral genomes of scAAV9.CB.SMN into the facial vein on Day 1 old mice rescues the SMN $\Delta$ 7 mouse model [19]. [Figure 2](#) shows the results of these studies, including staining of transduced spinal motor neurons, SMN expression levels, righting ability, and weight and survival curves. Approximately  $42 \pm 2\%$  of lumbar spinal motor neurons were transduced in scAAV9.CB.GFP treated mice. SMN transduction was shown by real time polymerase chain reaction (RT-PCR) in the mice. GFP transduction was observed by microscopy. Both constructs were in AAV9 and had transduction of motor neurons. SMN levels were increased as well, in brain, spinal cord, and muscle of scAAV9.CB.SMN-treated animals, compared to untreated SMN $\Delta$ 7 mice (although lower than wild type [WT] controls). SMN $\Delta$ 7 animals treated with either scAAV9.CB.SMN or scAAV9.CB.GFP on post-natal Day 1 were assessed for their righting ability and were compared to WT control mice and untreated mice. Wild type controls could right themselves quickly, whereas the SMN- and green fluorescent protein (GFP)-treated SMA animals showed difficulty at P5, however, by P13, 90% of SMN-treated animals could right themselves compared with 20% of GFP-treated

controls and 0% of untreated SMA animals. At P18, SMN-treated animals were larger than GFP-treated animals, but smaller than WT controls. Locomotive ability of the SMN-treated mice was nearly identical to WT controls, as assayed by open field testing and wheel running.

Survival of SMN-treated SMN $\Delta$ 7 animals compared with GFP-treated SMN $\Delta$ 7 animals was significantly improved. No GFP-treated control animals survived past P22 and had a median life span of 15.5 days. The weights of GFP mice peaked at P10 and then precipitously declined until death, while SMN mice showed a steady weight gain until around P40 with it stabilizing at 17 g (about half the weight of WT controls). The smaller size of corrected animals is likely related to the tropism and incomplete transduction of scAAV9, resulting in a ‘chimeric’ animal in which some cells were not transduced. Additionally, the smaller size suggests an embryonic role for SMN. Most remarkably, SMN-treated mice survived well past 250 days of age.

**Figure 2: Study Results, Including Staining of Transduced Spinal Motor Neurons, SMN Expression Levels, Righting Ability, and Weight and Survival Curves**

Source: Foust 2010 [19]

[figure not shown]
CNS = central nervous system; GFP = green fluorescent protein; SMN = survival motor neuron; WT = wild type

a) Shows transduced motor neurons in lumbar spinal cord

- b) Western Blots of SMN expression in CNS and muscle
- c) Improved righting ability of SMN-treated- similar to WT controls by P13
- d) SMN-treated are larger than GFP-treated at P18
- e) Survival of SMN-treated markedly improved compared to GFP- treated
- f) Body weight increased in SMN-treated vs GFP

Toxicology biodistribution studies were generated by the [REDACTED] [data on file]. In the non-Good Laboratory Practice (GLP) studies, 24 mice and 4 non-human primates (NHPs) were injected, by way of vascular delivery, with AVXS-101. To assess toxicity and safety, AVXS-101 was injected into P1 wild type Friend Virus B-Type (FVB) mice with either vehicle (3 males/6 females) or  $3.3 \times 10^{14}$  vg/kg of scAAV9.CB.SMN (6 males/9 females) via the facial temporal vein. This dose was previously shown to be most efficacious in the SMN $\Delta$ 7 mouse model [19]. P1 mice were used in anticipation of simulating potential clinical studies in infants. All mice survived the injection procedure and the initial 24-hour observation period without any signs of distress or weight loss. Body mass was measured and hands-on observations were performed weekly for the remainder of the study; neither revealed any difference between control and treated cohorts (Figure 3).

**Figure 3 Body Mass of Treated and Control Mice Showed No Difference**

At 60, 90 and 180 days post-injection, blood from the mice was collected for hematology studies including complete blood counts with differentials. At 90, 120 and 180 days post-injection, blood was collected for clinical chemistries assessment (alanine amino transferase [ALT], aspartate amino transferase [AST], alkaline phosphatase, creatinine, blood urea nitrogen [BUN], electrolytes, and creatine kinase [CK]). For histopathology, 13 mice were necropsied at 120 days post-injection and 8 mice at 180 days. There were no clinically significant results observed during from the hematology, clinical chemistry, and histopathology portions of the study and trends of both groups were comparable. Of note, no significant lesions were present in any brain or spinal cord sections, although, the sections were frozen and thicker than 5 microns which made cellular morphology obscure and subtle changes may not have been identified.

In the safety study for the 4 male *Cynomolgus* Macaques, animals were injected at 90 days of age to closely mimic the likely age of administration of treatment in SMA Type 1 infants. The AVXS-101 vector was administered 1 time by catheterization of the saphenous vein with a dose of  $6.7 \times 10^{13}$  vg/kg, which corresponds to the lowest dose tested for which SMN $\Delta$ 7 mice showed a significant increase of survival. Animals were followed for 6 months until they were sacrificed at approximately 9 months of age. No adverse effects were seen, and all clinical chemistries were normal. T-cell immune response was tested using Enzyme-linked ImmunoSpot (ELISpot) in peripheral blood mononuclear cells (PBMCs), and all were negative at 6 months post-injection.

In these non-GLP studies, the serum chemistry and hematology studies were unremarkable as was the histopathology assessment. The NHP patient animals mounted appropriate immune responses to capsid (but not to transgene), with very high transgene expression persisting at 6 months post-injection. In conclusion, these studies provide strong evidence that systemically-delivered scAAV9.CB.SMN is safe and well tolerated, even at the high doses required for penetration of the blood-brain barrier [data on file].

In pivotal GLP compliant 3-month mouse toxicology studies, the main target organs of toxicity were the heart and liver. Following intravenous infusion in the mouse, vector and transgene were widely distributed with the highest expression generally observed in heart and liver, and substantial expression in the brain and spinal cord. AVXS-101-related findings in the ventricles of the heart were comprised of dose-related inflammation, edema and fibrosis, and in the atrium, inflammation and thrombosis. Liver findings were comprised on hepatocellular hypertrophy, Kupffer cell activation, and scattered hepatocellular necrosis. A no observable adverse effect level (NOAEL) was not identified for AVXS-101-related heart and liver findings in the mouse, and the Maximum Tolerated Dose was defined as  $1.5 \times 10^{14}$  vg/kg, providing a safety margin of approximately 1.4-fold relative to the recommended therapeutic dose of  $1.1 \times 10^{14}$  vg/kg. The translatability of the observed findings in mice to primates is not known at this time.

## 5.4. Clinical Studies

First-in-human study AVXS-101-CL-101 is an ongoing 2-year study evaluating the efficacy and safety of AVXS-101 in 15 SMA Type 1 patients with 2 copies of *SMN2*. All patients have received a single IV dose of AVXS-101 in 2 cohorts: Cohort 1 (n = 3) received the low dose used in this study (equivalent to a dose that doubled mouse lifespan in the SMN $\Delta$ 7 Mouse potency assay) and Cohort 2 (n = 12) received the high dose used in this study (equivalent to a dose that restored mouse lifespan to greater than 200 days or “full life” in the SMN $\Delta$ 7 Mouse potency assay). The dose received by Cohort 2 patients in AVXS-101-CL-101 (proposed therapeutic dose) has been demonstrated to be equivalent to the dose to be used in the AVXS-101-CL-303 study by direct testing using improved analytical methods.

Preliminary data as of 15 September 2016 indicate that treatment with AVXS-101 results in broad improvements in survival, motor function, pulmonary function, and nutritional function. All patients in Cohort 2 (proposed therapeutic dose) showed improvements in survival, as defined by Finkel et al 2014 [21], with no deaths or requirements for permanent ventilation  $\geq 16$  hours/day for  $\geq 14$  consecutive days through 15 September 2016. The median age at last follow-up for Cohort 2 was 17.3 months, with the oldest patient at 27.4 months of age. One patient in Cohort 1 (low dose-cohort) had a pulmonary event of increased use of bi-level

positive airway pressure in advance of surgery related to hypersalivation, a condition experienced by some SMA patients. The event was determined by independent review to represent progression of disease and not related to AVXS-101.

As of September 15, 2016, improvements in motor function, as assessed by the CHOP-INTEND scores, were observed with mean increases of 9.0 points in Cohort 1 and 24.8 points in Cohort 2. The CHOP-INTEND scores in Cohort 2 were  $\geq 40$  points for 11/12 patients,  $\geq 50$  points for 9/12 patients, and  $\geq 60$  points (normal) for 3/12 patients.

As of September 15, 2016, patients in Cohort 2 consistently achieved and maintained key developmental motor milestones as summarized below:

- 11/12 patients achieved head control, 7/12 patients could roll, 11/12 patients could sit with support, and 8/12 patients could sit unassisted, including 1 patient whose achievement of this milestone was confirmed after 15 September 2016

## 6. TRIAL OBJECTIVES AND PURPOSE

### 6.1. Primary Objectives

The co-primary objectives are to:

- Determine the efficacy of AVXS-101 by demonstrating achievement of developmental milestone of functional independent sitting for at least 30 seconds at the 18 months of age study visit.
- Determine the efficacy of AVXS-101 based on survival at 14 months of age. Survival is defined by the avoidance of combined endpoint of either (a) death or (b) permanent ventilation, which is defined by tracheostomy or by the requirement of  $\geq 16$  hours of respiratory assistance per day (via non-invasive ventilatory support) for  $\geq 14$  consecutive days in the absence of an acute reversible illness, excluding perioperative ventilation. Permanent ventilation, so defined, is considered a surrogate for death.

### 6.2. Secondary Objective

The co-secondary objectives are to:

- Determine the effect of AVXS-101 on the on the ability to thrive defined as achieving all of the following at 18 months of age
  - Does not receive nutrition through mechanical support (e.g., feeding tube)
  - Ability to tolerate thin liquids as demonstrated through a formal swallowing test
  - Maintains weight ( $>$  third percentile for age and gender)
- Determine the effect of AVXS-101 on the ability to remain independent of ventilatory support, defined as requiring no daily ventilator support/usage at 18 months of age, excluding acute reversible illness and perioperative ventilation, as defined above through assessment of actual usage data captured from the device, for patients issued a Trilogy 100 BiPAP device

[REDACTED]

[REDACTED]

[REDACTED]

[REDACTED]

[REDACTED]

[REDACTED]

#### 6.4. Safety Objectives

The safety objectives are to:

- Evaluate the safety of AVXS-101 in patients with SMA Type 1
- Determine the safety of AVXS-101 based on the development of unacceptable toxicity defined as the occurrence of any Common Terminology Criteria for Adverse Events (CTCAE) [9] Grade 3 or higher, unanticipated, treatment-related toxicity.

## 7. INVESTIGATIONAL PLAN

[figure not shown]
### 7.1. Overall Study Design

This is a Phase 3, open-label, single-arm, single-dose study of AVXS-101 (gene replacement therapy) that will enroll up to twenty (20) patients with SMA Type 1 who may be either symptomatic or pre-symptomatic with no functional *SMN1* gene as well as 1 or 2 copies of *SMN2* and who are < 6 months (< 180 days) of age **at the time** of gene replacement therapy (Day 1). Enrolling up to twenty (20) patients under the broader enrollment criteria is projected to enable enrollment of at least 15 patients that meet the Intent-to-Treat Population (ITT) criteria. The ITT population is identified as symptomatic patients with bi-allelic *SMN1* deletions and 2 copies of *SMN2* without the *SMN2* gene modifier mutation (c.859G>C) who meet all other study enrollment criteria. In addition, the first 3 patients enrolled must meet the criteria for the Intent-to-Treat Population to enable a comparison of CHOP-INTEND scores at 1-month following gene replacement therapy to enable a comparison of patient response between AVXS-101-CL-303 patients and Cohort 2 patient results from the Phase 1 trial (AVXS-101-CL-101).

The study includes 3 study periods: screening, gene replacement therapy, and follow-up (Figure 4). During the screening period (Days -30 to -2), patients whose parent(s)/legal guardian(s) provide informed consent will undergo screening procedures to determine eligibility for study enrollment. Patients who meet the entry criteria will enter the in-patient gene replacement therapy period (Day -1 to Day 3). On Day -1, patients will be admitted to the hospital for pre-treatment baseline procedures. On Day 1, patients will receive a 1-time IV infusion of AVXS-101 at a dose equivalent to the dose received by the second dosing Cohort in the Phase 1 study over approximately 60 minutes and will undergo in-patient safety monitoring over the next 48 hours. Patients may be discharged 48 hours after gene replacement therapy, based on Investigator judgment. During the outpatient follow-up period (Days 4 to End of Study at 18 months of age), patients will return at regularly scheduled intervals for efficacy and safety assessments until the patient reaches 18 months of age. Any missed visit should be rescheduled as soon as possible, but within 7 days.

All post-treatment visits will be relative to the date on which gene replacement therapy is administered, except for the 14 and 18 months of age visits, which will be relative to the patient's date of birth. For the 14 and 18 months of age visits, the patient will return within 0 to 14 days **after** the date on which the patient reaches 14 and 18 months of age, respectively. The 18 months of age visit will also serve as the End of Study visit. After the End of Study visit, eligible patients will be asked to roll over into the long-term follow-up study.

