#### 14.1.2. Statistical Analysis Populations

##### 14.1.2.1. Intent-to-Treat Population (ITT)

The ITT population will consist of symptomatic patients with biallelic- deletion mutations of *SMN1* (exon 7/8 common homozygous deletions) and 2 copies of *SMN2* without the known gene modifier mutation (c.859G>C) who receive an IV infusion of AVXS-101 at < 180 days of age. The first 3 patients enrolled must meet the criteria for the Intent-to-Treat Population.

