### 14.2. Sample Size Calculation

This is a pivotal Phase 3, open-label, single-arm, single-dose, study assessing the efficacy and safety of AVXS-101 (gene replacement therapy) in up to twenty (20) patients with spinal muscular atrophy (SMA) Type 1 who meet enrollment criteria, may be either symptomatic or pre-symptomatic and are genetically defined by no functional survival motor neuron 1 gene (*SMN1*) with 1 or 2 copies of survival motor neuron 2 gene (*SMN2*) and who are < 6 months (< 180 days) of age **at the time** of gene replacement therapy (Day 1). Enrolling up to twenty (20) patients under the broader enrollment criteria is projected to enable enrollment of at least 15 patients that meet the Intent-to-Treat Population (ITT) criteria. The ITT population is identified as symptomatic patients with bi-allelic *SMN1* deletions and 2 copies of *SMN2* without the *SMN2* gene modifier mutation (c.859G>C) and will comprise the primary population for evaluation of the primary and secondary endpoints. Study power is based upon efficacy analysis of the ITT population. Furthermore, the first 3 patients enrolled must meet criteria for the Intent-To-Treat Population to enable a comparison of CHOP-INTEND scores at 1-month following gene replacement therapy to enable a comparison of patient response between AVXS-101-CL-303 patients and Cohort 2 patient results from the Phase 1 trial (AVXS-101-CL-101). Patients with 1 copy of *SMN2*, pre-symptomatic patients and patients with the *SMN2* gene modifier mutation (c.859G>C) and other permutations outside of those specified in the ITT population will be evaluated separately as part of additional subgroup analyses. Details of all analyses will be contained within the Statistical Analysis Plan.

The 2 co-primary efficacy endpoints will be assessed in sequence: The endpoint of functional independent sitting will be assessed first and, only if this assessment meets statistical significance will the endpoint of survival be assessed.

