Based upon the widely cited natural history of the disease (Pediatric Neuromuscular Clinical Research Network [PNCr]) [*Neurol.* 2014; 83(9):810-817], it is expected that no patients in this population would be expected to attain the ability to sit without support or accomplish other milestones (rolling over, standing, walking) prior to 18 months of age. Assuming that the true response rate for the primary endpoint is actually zero (or as low as 0.1%) in the population of interest of the historical control, the first co-primary efficacy endpoint hypothesis:

$$\begin{aligned} H_0: p_{AVXS-101} &= 0.1\% \\ &\textit{versus the alternative} \\ H_a: p_{AVXS-101} &> 0.1\%, \end{aligned}$$

where  $p$  is the proportion of functional independent sitting for at least 30 seconds at the 18 months of age study visit.

Based upon preliminary results from the ongoing Phase 1 clinical study AVXS-101-CL-101, at least 40% of treated symptomatic patients with bi-allelic deletions of *SMN1* and 2 copies of *SMN2* without the *SMN2* gene modifier mutation (c.859G>C) are expected to achieve the co-primary efficacy endpoint of functional independent sitting for at least 30 seconds at the 18 months of age study visit. With the assumption for the true response rate of AVXS-101 for

the primary endpoint being in the range of 30% - 40%, a sample size of 15 patients that meet ITT criteria will be enrolled and assuming approximately 30% of patients are excluded from analysis, would yield an ITT population that would provide power of > 90% to detect a significant difference from 0.1% with  $\alpha = 0.025$  using a 1-sided exact test for a binomial proportion.

The second co-primary efficacy endpoint hypothesis:

$$H_0: p_{AVXS-101} = p_{HISTORICAL-FINKEL}$$

*versus the alternative*

$$H_a: p_{AVXS-101} \neq p_{HISTORICAL-FINKEL}$$

where  $p$  is the proportion of patients surviving at 14 months of age.

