#### 14.3.2. Primary and Secondary Efficacy Analysis

Primary and secondary efficacy analyses will be based on the ITT population, those patients that are symptomatic with biallelic- deletion mutations of *SMN1* and 2 copies of *SMN2* without the *SMN2* gene modifier mutation (c.859G>C). These analyses are to test the superiority of AVXS-101 to the results from natural observation study (PNCR) [21].

The first co-primary efficacy hypothesis to be tested is:

$$\begin{aligned} \mathbf{H}_0: p_{AVXS-101} &= 0.1\% \\ &\textit{versus the alternative} \\ \mathbf{H}_a: p_{AVXS-101} &> 0.1\%, \end{aligned}$$

where  $p$  is the proportion of functional independent sitting for at least 30 seconds at the 18 months of age study visit.

The second co-primary efficacy hypothesis to be tested is:

$$\begin{aligned} \mathbf{H}_0: p_{AVXS-101} &= p_{HISTORICAL-FINKEL} \\ &\textit{versus the alternative} \\ \mathbf{H}_a: p_{AVXS-101} &\neq p_{HISTORICAL-FINKEL}, \end{aligned}$$

where  $p$  is the proportion surviving at 14 months of age.

Primary efficacy endpoints will be examined on the ITT population. Testing for the first co-primary endpoint, functional independent sitting will first be performed using 1-sided exact binomial test. Only if the null hypothesis of equality in proportion of functional independent sitting is rejected at  $p < 0.025$ , will the co-primary endpoint survival improvement be tested using 2-sided Fisher's Exact test on the ITT population, comparing to matched patients from natural observational study (PNCR). This hierarchy approach strongly protects the Type I error rate.

The hypothesis for both co-secondary efficacy endpoints to be tested is:

$$\begin{aligned} \mathbf{H}_0: p_{AVXS-101} &= 0.1\% \\ &\textit{versus the alternative} \\ \mathbf{H}_a: p_{AVXS-101} &> 0.1\%, \end{aligned}$$

where  $p$  is the proportion of patients maintaining the ability to thrive/are independent of ventilatory support.

One-sided exact binomial tests will be executed for secondary efficacy analyses on the ITT population.

A sensitivity analysis will be conducted by repeating the primary efficacy analysis on the efficacy completers analysis population.

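### The protocol defines its primary (ITT) population in two ways, and they disagree on whether a dosed infant who breached another entry criterion stays in the co-primary denominator.

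*Protocol*

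**What the plan says.** Two wordings of the ITT population stand in the current text.

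- **Synopsis (Methodology) and Section 7.1.** Symptomatic patients with bi-allelic SMN1 deletions and two SMN2 copies, without the "gene modifier mutation (c.859G>C) who meet all other study enrollment criteria".
- **Section 14.1.2.1.** Symptomatic patients with bi-allelic SMN1 deletions, glossed as "exon 7/8 common homozygous deletions", and two SMN2 copies, without the "known gene modifier mutation (c.859G>C) who receive an IV infusion of AVXS-101 at < 180 days of age". Meeting the remaining entry criteria is not required.

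The Synopsis statistical text and Sections 14.2 and 14.3.2 describe the population by symptomatic status and genotype only, again without the eligibility condition.

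The population carries the main conclusions. Section 14.2 says that it "will comprise the primary population for evaluation of the primary and secondary endpoints", and Section 14.3.2 says: "Primary efficacy endpoints will be examined on the ITT population". On size, "a sample size of 15 patients that meet ITT criteria will be enrolled", and the power text adds: "assuming approximately 30% of patients are excluded from analysis, would yield an ITT population". It does not say who those excluded patients are.

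**The concern.** Section 8.2 lists 19 exclusion criteria, covering among others oximetry, weight-for-age, recent infection, laboratory values, anti-AAV9 titer and gestational age. Take an infant with the right genotype who is symptomatic, is infused before 180 days, and is later found to have breached one of these. Section 14.1.2.1 keeps that infant in the co-primary denominator, and Section 7.1 removes the infant. Both cannot hold.

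The removing rule is the one to worry about. An analysis set that drops treated patients for eligibility deviations is a per-protocol set, whatever its label. Section 9.4 makes the trial open-label, so a deviation can be found or classified after the outcome is known. Infants who breach respiratory, weight or infection criteria are plausibly sicker, so removing them would tend to raise the sitting and survival rates. Both co-primary and both co-secondary tests use this set, and with about 15 patients one infant is visible in the result.

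**Working it through.** **1. The wordings side by side**

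| Condition | Synopsis Methodology, 7.1 | 14.1.2.1 | Synopsis statistics, 14.2, 14.3.2 |
|---|---|---|---|
| Symptomatic, genotype | yes | yes | yes |
| Infused at < 180 days | through the entry criteria | stated | not stated |
| Meets all other entry criteria | **required** | not required | not required |

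The one difference with consequences is the last row. It bites only if an infant is dosed despite failing another criterion.

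**2. The plan's own power figures**

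Inputs from Section 14.2: 15 patients less about 30% (15 × 0.7 = 10.5, so 10 or 11); sitting 30% to 40% against 0.1%, one-sided exact test at 0.025; survival 80% against 25% in 26 controls, two-sided Fisher test at 0.05.

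- Sitting rejects with one responder or more. Power = 1 − (1 − p)^n. At n = 10: 1 − 0.7^10 = 97.2% and 1 − 0.6^10 = 99.4%. At n = 11: 98.0% and 99.6%. The stated > 90% holds.
- Survival, exact Fisher power: 81.9% at n = 10 and 85.9% at n = 11. The stated > 80% holds.

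The power figures are sound, so the point concerns the denominator and not the sample size. With all 15 kept, power is 92.6% for survival and 99.5% or more for sitting.

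**3. Shift in a rate when one failing infant is dropped from 15**

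Shift = x/14 − x/15 = x/210.

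- x = 6: 6/210 = 2.9 points (40.0% to 42.9%)
- x = 8: 8/210 = 3.8 points
- x = 9: 9/210 = 4.3 points
- x = 12: 12/210 = 5.7 points (80.0% to 85.7%)

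**4. Survival test**

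The protocol gives 25% and 26 controls: 0.25 × 26 = 6.5, so 6 and 7 surviving controls are both tried. The treated counts and the single deviation are assumptions. Two-sided Fisher p-values, infant kept → infant dropped:

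| Treated survivors | 6/26 controls | 7/26 controls |
|---|---|---|
| 8/15 → 8/14 | 0.086 → 0.043 (flips) | 0.108 → 0.089 |
| 9/15 → 9/14 | 0.041 → 0.017 | 0.051 → 0.041 (flips) |
| 10/15 → 10/14 | 0.009 → 0.006 | 0.021 → 0.009 |
| 12/15 → 12/14 | 0.0008 → 0.0002 | 0.0014 → 0.0007 |

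Each flip needs one particular control count and treated survival of 53% or 60%. At a true survival of 80%, nine or fewer survivors among 15 has binomial probability 6.1%.

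**5. Sitting and co-secondary tests**

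All three are tested against 0.1%. With one responder the p-value is 1 − 0.999^n, which is 0.0149 at n = 15 and 0.0139 at n = 14. One responder suffices on either denominator, and a dropped non-responder cannot change that. The verdict would change only if the sole responder were the infant in dispute.

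**The case against.** The case against is substantial, and part of it stands.

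- **Eligibility is checked before dosing.** Screening, genetic reconfirmation for every patient, and local Day -1 laboratory results all precede infusion. Deviations should be few, and with none the two sets are identical. This stands, and it limits the expected effect.
- **ITT status must be known during enrollment.** The first three patients must qualify, and enrollment stops after the fifteenth who does. Section 14 also says the SAP is to be finalized before the first patient is enrolled. This reduces the room for post-hoc choice. It does not cover a breach discovered after dosing, and a SAP that chose one wording would still contradict the other section of the protocol.
- **The dedicated populations section has no eligibility clause**, and the other statistical texts agree with it. That is a good reason to prefer Section 14.1.2.1, but the protocol does not say that it prevails.
- **There are other sets.** The efficacy completers and all-enrolled populations are drawn from treated patients without an eligibility clause. They offer a cross-check but do not settle the primary analysis.

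Two stronger readings are tempting and not supported. A reader might infer that Section 7.1 admits infants who were never infused. Section 8.1 ties the age criterion to the time of infusion, and Section 14.1.2.3 defines all enrolled patients as those infused, so this largely fails. A reader might also infer that Section 14.1.2.1 uses a narrower deletion type. The parenthesis reads most naturally as a gloss on the same term, and no section treats other bi-allelic deletions differently.

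**Conclusion.** The inconsistency is real and sits in operative text. The primary population has two definitions, one of which removes treated infants for eligibility breaches. It affects only infants dosed despite failing an entry criterion other than symptomatic status, genotype or the age limit. The documents give no expected number of these.

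Per infant dropped from 15, the size is about 3 to 6 percentage points on a rate. A change in the survival verdict is possible only in the borderline cases shown, which rest on assumed control counts of 6 or 7 of 26 and on treated survival well below the planned 80%. At the planned effect the result is significant either way (p ≤ 0.0014). The documents do not support a broader inference that the trial's conclusions hang on the wording: sitting and both co-secondary tests are practically immune, and the power statements reproduce. The wording should be corrected because it leaves a possible exclusion bias open and is cheap to close.

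**What to change.** 1. Use the Section 14.1.2.1 definition everywhere: symptomatic, qualifying SMN1 deletions, two SMN2 copies without the modifier mutation, infused at < 180 days of age.
2. Delete the eligibility clause from the Synopsis methodology text and Section 7.1.
3. State that no infused infant meeting the Section 14.1.2.1 definition is removed for an eligibility deviation.
4. Use the same SMN1 deletion wording in every place.
5. Show the set that met all entry criteria as a sensitivity analysis only.

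The cost is a wording change and possibly slightly less favourable reported rates. The sample size does not change, and no dosing or clinical rule is touched.
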